#### **6.5.2.2. Protocol deviations**

All protocol violations that impact the safety of the patients and/or the conduct of a study and/or its evaluation will be reported. These include:

- Patients who are dosed on the study despite not satisfying the inclusion criteria
- Patients who develop withdrawal criteria whilst on the study but are not withdrawn
- Patients who receive the wrong treatment or an incorrect dose
- Patients who receive an excluded concomitant medication
- Deviations from GCP

The identification of these and other CSR-reportable deviations will be based on the inclusion/exclusion criteria or other criteria presented in the protocol.

#### **6.5.3. Study treatment compliance and exposure**

##### **Combinations A and F**

The following analyses will be based on the safety analysis set by treatment group using the data from the combined Phases 1b and 2 (Cohorts A1, A2, A3 and Cohorts F1, F2, F3) and the data from Phase 2 (Cohorts A4, A5, A6, A7, A8, A9, A10).

##### **Combinations B, C and D**

The following analyses will be based on the safety analysis set by treatment group using the data from Phase 1b and from Phase 2 separately and for each combination.

Cycle definitions for study drugs that are administered in combination apply to all the study drugs in the combination. I.e., cycle is patient-dependent, rather than study-drug-dependent when study drugs are administered in combination.

For Cycle X, actual cycle start date for each patient is

- the earliest start date of dosing in the Cycle X day 1 visit CRF exposure page, if the patient received study treatment on that visit (ie, any study drug with dose>0 at that visit)
- the first day of assessments in the Cycle X day 1 visit, if the patient did not receive study treatment on that visit (ie, all study drugs had dose=0 at that visit). Use start date in the exposure page if available; if start date is not available then use date of collection of vital signs on Cycle X day 1 visit.

Actual cycle end date for each patient is,

- for all cycles X except the last cycle, actual cycle end date = actual cycle (X+1) start date – 1 day
- for the last cycle, actual cycle end date = actual cycle start date + 28 – 1 day

**Cycle duration** (weeks) = (actual cycle end date – actual cycle start date + 1)/7

When summarizing exposure for each study drug, only cycles from first dose of study treatment until the last cycle with non-zero dose of at least one of the study drugs should be included.

Exposure may be summarized overall as dose received (cumulative dose, actual dose intensity) and as dose received relative to intended dose (relative dose intensity [RDI]).

The derivations below are provided for the following.

- Avelumab administered as a 1-hour IV infusion at a dose of 10 mg/kg once every 2 weeks in 4-week cycles
- Utomilumab administered as a 1-hour IV infusion at a dose of 20 mg, 100 mg, or 500 mg once every 4 weeks in 4-week cycles
- PF-04518600 administered as a 1-hour IV infusion at a dose of 0.1 mg/kg, 0.3 mg/kg, 1 mg/kg or 3 mg/kg once every 2 weeks in 4-week cycles
- PD 0360324 administered as a 30-min IV infusion at a dose of 50 mg, 100 mg, or 150 mg once every 2 weeks in 4-week cycles
- CMP-001 administered initially as 2 weekly 10 mg SC doses followed by IT dosing at weekly intervals for 5 additional doses of 10 mg. After the first 7 doses, CMP-001 will be administered as 10 mg IT every 2 weeks (Q2W)

#### **6.5.3.1. Exposure to avelumab**

The dose level for avelumab is calculated as actual dose administered/weight (mg/kg). The last available weight of the patient on or prior to the day of dosing will be used.

**Intended duration of treatment with avelumab (weeks) =**

$$(\text{end date} - \text{date of first dose of study drug} + 1) / 7,$$

where end date = start date of last cycle with non-zero dose of study drug + 28 – 1

**Duration of exposure to avelumab (weeks) =**

$$(\text{last dose date of avelumab} - \text{first dose date of avelumab} + 14) / 7$$

**Cumulative dose** is the sum of the actual doses of avelumab received overall.

**Actual Dose Intensity (DI)**

- Overall actual DI (mg/kg/4-week cycle) = [overall cumulative dose (mg/kg)] / [intended duration of treatment with avelumab (weeks)/4].

**Relative Dose Intensity (RDI)**

- Intended DI (mg/kg/4-week cycle) = [intended cumulative dose per cycle] / [intended number of 4-weeks in a cycle] = [20 (mg/kg)] / [1 (4-week cycle)] = 20 (mg/kg/4-week cycle)
- Overall RDI (%) =  $100 \times [\text{overall actual DI}] / [\text{intended DI}]$   
=  $100 \times [\text{overall actual DI}] / [20 \text{ (mg/kg/4-week cycle)}]$

### 6.5.3.2. Exposure to utomilumab

The dose level for utomilumab is calculated as actual dose administered (mg).

**Intended duration of treatment with utomilumab (weeks) =**

$$(\text{end date} - \text{date of first dose of study drug} + 1) / 7,$$

where end date = start date of last cycle with non-zero dose of study drug + 28 – 1

**Duration of exposure to utomilumab (weeks) =**

$$(\text{last dose date of utomilumab} - \text{first dose date of utomilumab} + 28) / 7$$

**Cumulative dose** is the sum of the actual doses of utomilumab received overall.

**Actual Dose Intensity (DI)**

- Overall actual DI (mg/4-week cycle) = [overall cumulative dose (mg)] / [intended duration of treatment with utomilumab (weeks)/4]

**Relative Dose Intensity (RDI)**

- Intended DI (mg/4-week cycle) = [intended cumulative dose per cycle] / [intended number of 4-weeks in a cycle] = [d (mg)] / [1 (4-week cycle)] = d (mg/4-week cycle)

- Overall RDI (%) =  $100 \times [\text{overall actual DI}] / [\text{intended DI}]$   
=  $100 \times [\text{overall actual DI}] / [d \text{ (mg/4-week cycle)}]$

where d=20, 100 or 500.

### 6.5.3.3. Exposure to PF-04518600

The dose level for PF-04518600 is calculated as actual dose administered/weight (mg/kg). The last available weight of the patient on or prior to the day of dosing will be used.

**Intended duration of treatment with PF-04518600 (weeks) =**

(end date–date of first dose of study drug +1)/7,

where end date = start date of last cycle with non-zero dose of study drug + 28 – 1

**Duration of exposure to PF-04518600 (weeks) =**

(last dose date of PF-04518600 – first dose date of PF-04518600 + 14)/7

**Cumulative dose** is the sum of the actual doses of PF-04518600 received overall.

### Actual Dose Intensity (DI)

- Overall actual DI (mg/kg/4-week cycle) =  $[\text{overall cumulative dose (mg/kg)}] / [\text{intended duration of treatment with PF-04518600 (weeks)/4}]$ .

### Relative Dose Intensity (RDI)

- Intended DI (mg/kg/4-week cycle) =  $[\text{intended cumulative dose per cycle}] / [\text{intended number of 4-weeks in a cycle}] = [2 \times d \text{ (mg/kg)}] / [1 \text{ (4-week cycle)}] = 2 \times d \text{ (mg/kg/4-week cycle)}$
- Overall RDI (%) =  $100 \times [\text{overall actual DI}] / [\text{intended DI}]$   
=  $100 \times [\text{overall actual DI}] / [2 \times d \text{ (mg/kg/4-week cycle)}]$

where d=0.1, 0.3, 1 or 3.

### 6.5.3.4. Exposure to PD 0360324

The dose level for PD 0360324 is calculated as actual dose administered (mg).

**Intended duration of treatment with PD 0360324 (weeks) =**

(end date–date of first dose of study drug +1)/7,

where end date = start date of last cycle with non-zero dose of study drug + 28 – 1

**Duration of exposure to PD 0360324 (weeks) =**

(last dose date of PD 0360324 – first dose date of PD 0360324 + 14)/7

**Cumulative dose** is the sum of the actual doses of PD 0360324 received overall.

### Actual Dose Intensity (DI)

- Overall actual DI (mg/4-week cycle) = [overall cumulative dose (mg)] / [intended duration of treatment with PD 0360324 (weeks)/4].

### Relative Dose Intensity (RDI)

- Intended DI (mg/4-week cycle) = [intended cumulative dose per cycle] / [intended number of 4-weeks in a cycle] = [2×d (mg)] / [1 (4-week cycle)] = 2×d (mg/4-week cycle)
- Overall RDI (%) =  $100 \times [\text{overall actual DI}] / [\text{intended DI}]$   
=  $100 \times [\text{overall actual DI}] / [2 \times d \text{ (mg/4-week cycle)}]$

where d=50, 100 or 150.

### 6.5.3.5. Exposure to CMP-001

The dose level for CMP-001 is calculated as actual dose administered (mg).

**Intended duration of treatment with CMP-001 (weeks) =**

$$(\text{end date} - \text{date of first dose of study drug} + 1) / 7,$$

where end date = start date of last cycle with non-zero dose of study drug + 28 – 1

**Duration of exposure to CMP-001 (weeks) =**

$$(\text{last dose date of CMP-001} - \text{first dose date of CMP-001} + d) / 7,$$

where d=7 if last dose date of CMP-001 – first dose date of CMP-001  $\leq 39$  (corresponding to the study day after the first 6 weekly doses of CMP-001, before dosing schedule changes to Q2W, plus window), or d=14 otherwise.

**Cumulative dose** is the sum of the actual doses of CMP-001 received overall.

### Actual Dose Intensity (DI)

- Overall actual DI (mg/4-week cycle) = [overall cumulative dose (mg)] / [intended duration of treatment with CMP-001 (weeks)/4]

### Relative Dose Intensity (RDI)

- Intended DI (mg/4-week cycle) = [intended cumulative dose per cycle] / [intended number of 4-weeks in a cycle] = [d (mg)] / [1 (4-week cycle)] = d (mg/4-week cycle)
- Overall RDI (%) =  $100 \times [\text{overall actual DI}] / [\text{intended DI}]$   
=  $100 \times [\text{overall actual DI}] / [d \text{ (mg/4-week cycle)}]$

where

- d=40 if last dose date of CMP-001 – first dose date of CMP-001  $\leq 25$  (corresponding to Cycle 1 dosing); else

- d=30 if  $26 \leq$  last dose date of CMP-001 – first dose date of CMP-001  $\leq 50$  (corresponding to Cycle 2 dosing), else
- d=20

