#### **Combination F**

- Cohort F1 (Phase 1b/Phase 2 SCCHN): avelumab 10 mg/kg IV Q2W in combination with 10 mg CMP-001
- Cohort F2 (phase 1b/ Phase 2 SCCHN): avelumab 10 mg/kg IV Q2W in combination with 10 mg CMP-001 and 100 mg utomilumab IV Q4W
- Cohort F3 (Phase 1b/ Phase 2 SCCHN): avelumab 10 mg/kg IV Q2W in combination with 10 mg CMP-001 and 0.3 mg/kg PF-04518600 IV Q2W

CMP-001 will be administered initially as 2 weekly subcutaneous (SC) doses followed by intra tumoral (IT) dosing at weekly intervals for 5 additional doses. After the first 7 doses, CMP-001 will be administered IT every 2 weeks (Q2W) (all cohorts).

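### The CMP-001 overall relative dose intensity divides a whole-treatment average by the planned dose of the last cycle only, so it is overstated for patients dosed beyond Cycle 1

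*SAP*

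**What the plan says.** Section 6.5.3 gives the CMP-001 schedule on which the derivations rest: "CMP-001 administered initially as 2 weekly 10 mg SC doses followed by IT dosing at weekly intervals for 5 additional doses of 10 mg", then "After the first 7 doses, CMP-001 will be administered as 10 mg IT every 2 weeks (Q2W". Section 3.4.1 (Combination F) gives the same schedule for all three cohorts: "After the first 7 doses, CMP-001 will be administered IT every 2 weeks (Q2W) (all cohorts".

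Section 6.5.3.5 builds the relative dose intensity (RDI) in four steps.

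- Intended duration runs from the first dose to the end of the last dosed 28-day cycle: "where end date = start date of last cycle with non-zero dose of study drug + 28 – 1".
- Cumulative dose "is the sum of the actual doses of CMP-001 received overall".
- Actual dose intensity (DI) is the ratio of the two, in 4-week units: "Overall actual DI (mg/4-week cycle) = [overall cumulative dose (mg)] / [intended duration of treatment with CMP-001 (weeks)/4", closing bracket omitted.
- Overall RDI is 100 times actual DI divided by d. The rule reads "d=40 if last dose date of CMP-001 – first dose date of CMP-001" is no more than 25 days. Otherwise d is 30 when the gap is 26 to 50 days, and 20 when it is longer. The SAP ties the first two values to Cycle 1 and Cycle 2 dosing.

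For utomilumab, Section 6.5.3.2 limits the planned dose to three values, "where d=20, 100 or 500", and Section 6.5.3 lists the same three. Section 3.4.1 assigns 50 mg to cohorts D12, D22 and D32.

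**The concern.** A relative dose intensity should be 100% for a patient who receives every planned dose, however long treatment lasts. That requires the received and the planned amount to cover the same period. Here the received amount is averaged over all cycles and the planned amount belongs to one cycle.

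The other four drugs are given a constant planned amount per 4-week cycle, so the same template does no harm there. CMP-001 is front-loaded, so from Cycle 2 onward the last cycle's plan is smaller than the average plan and the ratio comes out too high. The excess also changes with time on treatment, so two equally compliant patients can receive different values.

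What is at stake is the reading of CMP-001 compliance in cohorts F1 to F3. The dose-reduction summary in Section 6.5.3.6 counts only non-zero doses below 90% of plan, so it cannot show an omitted dose. Section 6.6.1.2 lists interruption tables for the other four drugs but none for CMP-001. The version history (version 4) gives as the reason for dropping the summaries of omissions and delays that overall RDI captures them. For CMP-001 it does so only in part.

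**Working it through.** **Inputs.** Each dose is 10 mg. Nominal days from first dose are 0, 7, 14, 21, 28, 35, 42, then every 14 days (56, 70, 84, ...), from Sections 3.4.1 and 6.5.3. Cycles last 28 days. I take the last cycle to be the last one with a CMP-001 dose, because the SAP uses the term study drug for a single agent and study treatment for the combination.

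**Reproducing d.** Days 0 to 27 hold four doses (40 mg), days 28 to 55 hold three (30 mg), and each later cycle holds two (20 mg). The SAP's 40, 30 and 20 are therefore the planned amounts of Cycle 1, Cycle 2 and any later cycle.

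**Full compliance through k cycles.** SAP RDI = 100 × (cumulative mg / k) / d.

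| k | Planned and received, mg | Average per cycle | d | SAP RDI |
|---|---|---|---|---|
| 1 | 40 | 40 | 40 | 100% |
| 2 | 70 | 35 | 30 | 116.7% |
| 3 | 90 | 30 | 20 | 150% |
| 4 | 110 | 27.5 | 20 | 137.5% |
| 6 | 150 | 25 | 20 | 125% |
| 12 | 270 | 22.5 | 20 | 112.5% |

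For k of 3 or more the planned total is 40 + 30 + 20(k − 2) = 20k + 30 mg. Dividing by k and then by 20 gives RDI = 100 × (1 + 1.5/k). The excess peaks at k = 3 and shrinks after that.

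**Missed doses.** Take the first dose as given and the last dose given as falling in Cycle k. The correct value is doses received over doses planned through Cycle k.

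| Last dose in cycle | Received / planned | SAP RDI | Correct RDI |
|---|---|---|---|
| 2 | 6 / 7 | 60/2/30 = 100% | 85.7% |
| 3 | 6 / 9 | 60/3/20 = 100% | 66.7% |
| 4 | 8 / 11 | 80/4/20 = 100% | 72.7% |
| 6 | 12 / 15 | 120/6/20 = 100% | 80.0% |
| 12 | 24 / 27 | 240/12/20 = 100% | 88.9% |

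From Cycle 3 on, the surplus in the planned total over 20k is 30 mg, or three doses, so exactly three omissions bring the SAP value down to 100%. In Cycle 2 the surplus over 2 × 30 is 10 mg, or one dose. A fourth omission through Cycle 3 gives 50/3/20 = 83.3%, against a correct 5/9 = 55.6%.

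**Utomilumab.** The sets do not match: Section 3.4.1 uses 50 mg in D12, D22 and D32, while Sections 6.5.3 and 6.5.3.2 allow only 20, 100 or 500 mg. No listed d fits those three cohorts.

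**The case against.** The best defence concerns importance. RDI enters no hypothesis test, DLT rule or response analysis. Phase 2 of Combination F has no formal decision rules, and Section 6.5.3 says only that exposure may be summarized. The fault touches one descriptive variable for one drug in about 60 patients. Patients whose last CMP-001 dose falls in Cycle 1 get the right value on nominal dates. Cumulative dose, actual DI and duration of exposure do not use the 40/30/20 value and are unaffected, and discontinuations of CMP-001 are tabulated separately. All of this stands and sets the weight of the point. It does not repair the formula: the SAP labels the result as overall and provides no by-cycle calculation.

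Some stronger readings go further than the document allows.

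- A reader might infer that missed doses vanish. They do not. Masking to 100% or more stops at three omissions (one if the last dose is in Cycle 2), and further omissions lower the figure, though it stays too high.
- A reader might infer that comparisons of safety or activity across F1 to F3 are distorted. All three cohorts share the schedule and the formula, so a difference between cohorts would arise only through differing treatment duration, and the SAP gives no figure for that.
- A reader might infer that 50 mg utomilumab patients would be reported at 250% or 50%. That assumes a programmer applies a dose the patient was not assigned, and the SAP does not say so. It shows only an incomplete list.

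**Conclusion.** The CMP-001 formula is wrong as written for patients whose last dose falls after Cycle 1. On nominal dates it overstates RDI by a factor of 1.167 when the last dose is in Cycle 2 and 1 + 1.5/k when it is in Cycle k from 3 on, with the maximum of 1.5 at Cycle 3.

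The 150% peak is a nominal-date value, not a strict ceiling. Because d switches on elapsed days, a seventh dose that slips to 51 days after the first still lies within two cycles but takes d = 20, giving 70/2/20 = 175%.

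The figures also rest on reading the end of the intended duration as the last cycle with CMP-001. If it ran to the last cycle of any drug in the combination, patients who stop CMP-001 early would have different values. Those dosed to the end would not.

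This should be fixed before the exposure tables are produced. It does not threaten the primary analysis. The utomilumab mismatch is separate and minor.

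**What to change.** In Section 6.5.3.5, replace the RDI definition with RDI = 100 × cumulative dose / intended cumulative dose. Take the intended cumulative dose over the same intended duration from the SAP's own schedule: 40 mg for the first 4-week cycle, 30 mg for the second and 20 mg for each later one. Drop the rule that picks one d from the last dose date. Full compliance then gives 100% at every duration, and 6 of 9 doses gives 66.7%.

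Separately, reconcile the utomilumab doses in Section 3.4.1 (Combination D) with Sections 6.5.3 and 6.5.3.2, so that d equals each cohort's assigned dose.

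The cost is SAP wording and one derived variable for CMP-001, plus the corrected list for utomilumab. No new data are needed, and neither change takes a position on dose or schedule.

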#### **6.5.3.6. Dose reductions**

Applicable only to avelumab, utomilumab, PF-04518600, PD 0360324, and CMP-001.

Dose reduction is defined as actual non-zero dose < 90% of the planned dose. The number and percentage of patients with at least one dose reduction as well as a breakdown of dose reductions (1, 2, 3,  $\geq 4$ ) will be summarized.

#### **6.5.4. Concomitant medications and non-drug treatments**

##### **Combinations A and F**

The following analyses will be based on the safety analysis set by treatment group using the data from the combined Phases 1b and 2 (Cohorts A1, A2, A3 and Cohorts F1, F2, F3) and the data from Phase 2 (Cohorts A4, A5, A6, A7, A8, A9, A10).

##### **Combinations B, C and D**

The following analyses will be based on the safety analysis set by treatment group using the data from Phase 1b and from Phase 2 separately and for each combination.

**Concomitant medications** are medications, other than study drugs, which started prior to first dose date of study treatment and continued during the on-treatment period as well as those started during the on-treatment period.

Concomitant medications will be summarized from the ‘General Concomitant Medications’ eCRF page.

Summary of concomitant medications will include the number and percentage of patients by Anatomical Therapeutic Chemical (ATC) Classification level 2 and preferred term. A patient will be counted only once within a given drug class and within a given drug name, even if he/she received the same medication at different times. If any concomitant medication is classified into multiple ATC classes, the medication will be summarized separately under each of these ATC classes. The summary tables will be sorted on decreasing frequency of drug class and decreasing frequency of drug name in a given drug class. In case of equal frequency regarding drug class (respectively drug name), alphabetical order will be used. In case any specific medication does not have ATC classification level 2 coded term, it will be summarized under ‘Unavailable ATC classification’ category.

#### **6.5.5. Subsequent anti-cancer therapies**

##### **Combinations A and F**

The following analyses will be based on the safety analysis set by treatment group using the data from the combined Phases 1b and 2 (Cohorts A1, A2, A3 and Cohorts F1, F2, F3) and the data from Phase 2 (Cohorts A4, A5, A6, A7, A8, A9, A10).

### **Combinations B, C and D**

The following analyses will be based on the safety analysis set by treatment group using the data from Phase 1b and from Phase 2 separately and for each combination.

Number and percentage of patients with any anti-cancer therapy after discontinuation will be tabulated overall and by type of therapy based on the data collected from the 'Follow-up Cancer Therapy', 'Follow-up Radiation Therapy' and 'Follow-up Surgery' eCRF pages.

## **6.6. Safety Summaries and Analyses**

The Safety Analysis Set will be the primary population for safety evaluations.

### **Combinations A and F**

The following analyses will be based on the safety analysis set by treatment group using the data from the combined Phases 1b and 2 (Cohorts A1, A2, A3 and Cohorts F1, F2, F3) and the data from Phase 2 (Cohorts A4, A5, A6, A7, A8, A9, A10).

### **Combinations B, C and D**

The following analyses will be based on the safety analysis set by treatment group using the data from Phase 1b and from Phase 2 separately and for each combination.

#### **6.6.1. Adverse events**

Treatment-emergent adverse events (TEAEs) are those events with onset dates occurring during the on-treatment period as defined in Section 3.5.1.

All analyses described will be based on TEAEs (started during the on-treatment period) if not otherwise specified. The AE listings will include all AEs (whether treatment-emergent or not). AEs outside the on-treatment period will be flagged in the listings.

- **Related Adverse Events:** adverse events with relationship to study treatment (as recorded on the AE eCRF page, Relationship with study treatment = Related) reported by the investigator and those of unknown relationship (ie, no answer to the question 'Relationship with study treatment'). Related AEs are those related to any study drug (ie, at least one of the study drugs).
- **Serious Adverse Events (SAE):** serious adverse events (as recorded on the AE eCRF page, Serious Adverse Event = Yes).
- **Adverse Events Leading to Interruption of Study Treatment:** adverse events leading to interruption of study treatment (as recorded on the AE eCRF page, Action taken with study treatment = Drug interrupted). The eCRF does not allow for a clear separation between interruption of an infusion and delays of administration for a parenteral drug as

both are recorded using the same term on the eCRF (“Drug interrupted”). IRRs will be excluded in the analysis of AEs leading to Drug Interruption in case they only led to an interruption of the infusion.

- **Adverse Events Leading to Permanent Treatment Discontinuation:** adverse events leading to permanent discontinuation of study treatment (as recorded on the AE eCRF page, Action taken with study treatment = Drug withdrawn).
- **Adverse Events Leading to Death:** adverse event leading to death (as recorded on the AE eCRF page, Outcome = Fatal, as well as AEs of Grade 5).
- **Immune-related Adverse Events (irAE):** irAEs (as identified according to the methodology outlined in Appendix 1 for a pre-specified search list of MedDRA PTs, documented in the Safety Review Plan (SRP) and finalized for analysis of the current study data prior to DB lock)
- **Infusion-related Reactions (IRR):** IRRs (as identified according to the methodology outlined in Appendix 2 for a pre-specified search list of MedDRA PTs documented in the SRP and finalized for analysis of the current study data prior to DB lock).

Unless otherwise specified, AEs will be summarized by number and percentage of patients with the AE in the category of interest as described above, by treatment group, primary SOC and PT in decreasing frequency based on the frequencies observed.

Each patient will be counted only once within each SOC or PT. If a patient experiences more than one AE within a SOC or PT for the same summary period, only the AE with the strongest relationship or the worst severity, as appropriate, will be included in the summaries of relationship and severity.

